4.2.1 Protocol Number

4.2.2 Investigator Identification

4.2.2.1 Institution and affiliate name.

4.2.2.2 Investigator's name.

4.2.3 Patient Identification

4.2.3.1 Patient's initials and chart number.

4.2.3.2 Patient's Social Security number.

4.2.3.3 Patient demographics

4.2.3.3.1 Sex

4.2.3.3.2 Birth date (mm/yyyy)

4.2.3.3.3 Race

4.2.3.3.4 Ethnicity

4.2.3.3.5 Nine-digit ZIP code

4.2.3.3.6 Method of payment

4.2.3.4 Patient sequence number assigned at pre-registration.

4.2.4 Eligibility Verification

Patients must meet all of the eligibility requirements listed in Section [3](#). An eligibility checklist has been appended to the protocol. A confirmation of registration will be forwarded by the ECOG-ACRIN Operations Office - Boston.

4.2.5 Stratification Factors

4.2.5.1 Marker status and treatment plan

- ER+ or PR+, HER2-, plan to treat with endocrine therapy alone

- ER+ or PR+, HER2-, plan to treat with chemotherapy (with or without endocrine therapy)
- ER- or PR-, HER2-
- HER2+

4.2.5.2 Number of involved organ systems (beyond the primary tumor, chest wall, and locoregional nodes, i.e., axilla, internal mammary, supraclavicular).

- Single organ system with distant disease
- More than one organ system with distant disease (regional nodes in the axillary, supraclavicular, and internal mammary locations are not considered distant sites).

4.2.6 Additional Requirements

4.2.6.1 Patients must provide a signed and dated, written informed consent form.

4.2.6.2 Pathological materials and blood samples should be submitted as indicated in Section [9](#) for banking per patient consent.

NOTE: The establishment of research rates within the institution's financial office must be in place prior to the performance of the additional biopsies. See Section [9.4](#) for guidelines.

NOTE: ECOG-ACRIN requires that biological samples submitted from patients participating in E2108 be entered and tracked via the online ECOG-ACRIN Sample Tracking System (STS). Any case reimbursements associated with sample submissions must not be captured if samples are not logged into STS. See Section [9.3](#).

NOTE: Institutions outside of the United States and Canada must confer with the receiving laboratory and the ECOG-ACRIN Operations Office - Boston regarding logistics for submission of fresh samples.

4.3 Instructions for Patients who Do Not Start Assigned Protocol Treatment

If a patient does not randomize to Step 2, please document the reason on the E2108 Step 1 Vital Status form and submit this form through 5 years per the E2108 forms submission schedule.

After randomization to step 2, if a patient does not receive the assigned protocol treatment, follow-up data will still be collected and must be submitted according to the instructions in the E2108 Forms Packet. Document the reason for not starting protocol treatment on the off-treatment form.

5. Treatment Plan

5.1 Treatment

Rev. 7/12, 2/13

Patients may be registered to Step 1 (Arm S) prior to initiation of systemic therapy OR up to 30 weeks after start of systemic therapy. Full local and distant disease evaluation (clinical and radiological) must have been performed a maximum of 8 weeks prior to start of systemic therapy. Scans performed within 4 weeks following the start of systemic therapy, but prior to registration, will be acceptable as baseline studies, but complete imaging prior to start of therapy is preferred. If radiation at a distant site was required prior to start of systemic therapy, scans can be 8 weeks prior to or 4 weeks following the start of radiation.

Rev. 7/13

All baseline studies documenting extent of disease must be repeated prior to Step 2 randomization. Patients with progressive disease per the criteria in Section [3.2.4](#) will not randomize to Step 2 but will be followed for survival. Those with stable or responsive disease will be randomized to receive elective local therapy (Arm B) versus the palliative local therapy (Arm A) when/if needed. Systemic therapy will continue on both treatment arms as directed by the treating physician. Patients who had advanced local disease at registration can be randomized if the local disease is now considered operable by conventional criteria.

Rev. 2/13

5.1.1 Systemic Therapy (Step 1: Arm S)

Optimal systemic therapy will be determined by the treating physician based on tumor profile, patient age, and menopausal status. The use of NCCN or equivalent guidelines are encouraged. First-line systemic therapy may also be offered on a Phase II or III trial, and may be randomized at Step 2, as long as there is no evidence of progression (see Section [6.1](#)). A change in systemic therapy is allowed for toxicity or at physician discretion (e.g. switch from chemotherapy to endocrine therapy), as long as the change is not for disease progression. However, randomization at end of 1st regimen is encouraged.

Rev. 7/13

5.1.2 Local Therapy Treatments (Step 2: Arms A and B)

5.1.2.1 Arm A: Continued Systemic Therapy

Systemic therapy will continue as directed by the treating physician.

Local therapy should be offered to patients only if needed for palliation of symptoms such as tumor ulceration, pain, bulky adenopathy causing arm symptoms, and other similar situations where therapy is designed specifically to address symptoms at the local site. It may consist of radiotherapy alone, surgery alone, or the combination.

5.1.2.2 Arm B: Early Local Therapy

Surgery is to occur no later than 10 weeks after randomization.

Surgical treatment will be chosen by patient and physician according to the criteria that are generally accepted for breast conserving therapy (BCT) or total mastectomy

Rev. 7/12
Rev. 4/14
Rev. 4/14

Rev. 7/12

(TM). If BCT is chosen, free surgical margins must be achieved with re-excision or mastectomy (no minimum margin width is required). Axillary management should parallel that used for non-metastatic breast cancer. Axillary dissection is required if clinical and radiologic evaluation at initial registration was suggestive of axillary disease and axillary radiation is not planned. For women not receiving axillary dissection, sentinel node biopsy should document an axillary nodal burden of 1-2 involved lymph nodes (i.e. ACOSOG Z-11 criteria may be applied if axillary radiation is not planned). For women undergoing TM, reconstructive surgery will be allowed at the discretion of the treating physician, recognizing that this may delay the continuation of systemic therapy and complicate radiation planning. Surgical quality assurance will be coordinated with the ECOG-ACRIN Surgery Committee.

Systemic therapy may resume after recovery from surgery as directed by the treating physician. Systemic therapy will continue directed by the treating physician.

Following surgery, radiotherapy is to be given as outlined in Section [5.3](#).

5.2 Health-Related Quality of Life Assessment

Rev. 4/14

Overall health-related quality of life (physical, functional, emotional and social well-being) will be assessed by administering the FACT-G. Breast cancer-specific concerns will be assessed by administering the Breast Cancer subscale of the FACT. Participants will complete the 27-item FACT-G, the 10-item FACT-Breast subscale and 9 additional items that have been written for this trial. We will use the FACT-B TOI to assess HRQL. The FACT-B TOI is calculated by summing the physical well-being (7 items), functional well-being (7 items) and breast cancer-specific (10 items) scales from the FACT. In addition, five items from the FACT Breast cancer subscale and four items from the FACT-G have been selected a priori for individual item analysis to assess differences in pain, body image, and worry between treatment arms. Given the lack of an available scale to assess these concerns in a tailored and concise manner, we have written additional items for the FACT Breast cancer subscale to capture these concerns (four items to assess lymphedema, one item to assess worry about tumor growth, two items to assess discomfort in the breast and chest wall, and two items to assess the effects of tumor nodules and ulcers on functional well-being). Because these items are exploratory, we will examine the psychometric properties of each item as well as composite scores (eg. summation of lymphedema items) prior to calculating treatment arm comparisons. In addition we will use data collected from this trial to validate these items.

Rev. 4/14

The FACT-Breast and additional items (referred to as the FACT-Breast + Local Symptoms-9 or FACT-B + LS-9) to assess HRQL will be administered at five time points: step 1: registration (+/- 14 days); step 2: randomization ; six months post-randomization (+/- 14 days); 18 months post-randomization (+/- 14 days); and 30 months post-randomization (+/- 14 days). It is anticipated that participants in the early local therapy arm (Arm B) will have completed surgery and radiation therapy at approximately 6 months post-randomization and will

likely still experience acute treatment-related symptoms, while most participants in the palliative local therapy arm (Arm A) will not have received any treatment as of 6 months post-randomization.

Therefore, a comparison at 18 months post-randomization on the FACT-B TOI score will be used as the primary HRQL endpoint analysis. A second HRQL analysis will examine FACT-B scores at about 30 months post-randomization. We hypothesize that the HRQL for the breast/chest wall items will be better for the control arm at the 6 month timepoint, and will be better in the experimental arm at the 18 month time point. An additional timepoint for Arm A patients will be at the point of decision for local therapy. No formal comparative analysis is planned for this data, but it will serve to document the degree of symptoms that trigger the decision for palliative therapy in the control arm.

Timing of FACT-B + LS-9 Administration

Rev. 4/14
Rev. 4/14

Questionnaires*	Step 1: Registration (+/- 14 days)	Step 2: Randomization	At 6 months post randomization (+/- 14 days)	At 18 months post randomization (+/- 14 days)	At 30 months post- randomization (+/- 14 days)	At decision for early local therapy (prior to surgery – Arm A patients only) (+/- 14 days)	Approximate time to complete
FACT-B + LS-9	X	X	X	X	X	X	15 minutes

* Please note that the QOL questionnaire is only available in English.

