5.2.1 QOL Instrument Administration Instructions

- 5.2.1.1 The questionnaires must be administered at the timepoints listed above. The patient should be instructed to respond to the questionnaires in terms of his/her experience during the time frame specified on each questionnaire.
- 5.2.1.2 The CRN/CRA should read the instructions printed on the questionnaire to the patient and ensure the patient understands the instructions. It is important to assure the patient that all material on the questionnaire is confidential and will not be shared with the health care team and that it will not become part of the medical record. It is permissible to assist the patient with the completion of the questionnaires as long as the staff person does not influence the patient's responses.
- 5.2.1.3 Whenever possible, the HRQL assessment should be administered at the clinic visit before the patient is seen by the physician, before evaluations are performed and before test results are shared with the patient. In the event that the questionnaires are not administered at the clinic visit, the HRQL data can be collected by telephone or mail as backup methods provided that HRQL data is captured prior to initiation of treatment.

- 5.2.1.4 Assistance in reading the questionnaire is permitted if the patient is unable to complete the questionnaire on his/her own (e.g. difficulty in reading, elderly). It is important not to influence the response of the patient. Note why the patient required assistance and the type of assistance given.
- 5.2.1.5 Patients should be instructed to answer all the questions regardless of whether the symptoms or conditions asked about are related to the cancer or cancer treatment. Discourage family members from being present during questionnaire completion or from influencing the patient's responses. The questionnaires must be reviewed by the protocol nurse or research coordinator as soon as the patient completes them to ensure all items were marked appropriately. If the patient has marked more than one answer per question, ask the patient which answer best reflects how they are feeling. If the patient has skipped a question or questions, the patient should be asked if he/she would like to answer it. If the patient refuses, it should be indicated on the questionnaire that he/she declined to answer the item.

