Rev. 7/12 3. In Arm A patients, if a decision is made to deliver palliative local therapy, a complete local-regional assessment must document reason for palliative treatment and must include same imaging tests that were performed at start of systemic therapy, if possible. If not possible, (e.g. denied by insurance), other appropriate tests can be substituted that will evaluate all prior sites of disease and will address any new signs/symptoms.

Rev. 4/14 4. [Deleted in Addendum #2]

Rev. 7/12 5. Patients who are not randomized will be followed for survival for 5 years post registration.

Rev. 7/12 6. Collect only if performed as part of standard clinical assessments and covered by third party reimbursement.

Rev. 7/12, 7/13 7. Collect prior to randomization.

Rev. 4/14 8. Pathology reports confirming diagnosis of breast cancer and, if only one metastatic lesion is present, the metastatic site must be submitted to the ECOG-ACRIN Operations Office - Boston within one month of registration to step 1.

Rev. 4/14 9. Breast imaging studies with mammogram OR ultrasound OR breast MRI measurement are requested at baseline (see 3.1.4 and 7.1 for definition of baseline evaluation). However, if in the judgment of the physician, physical exam provides sufficient documentation of tumor size and T stage, and breast imaging has not been performed in the baseline period, the patient is still eligible. If possible, the same imaging studies should be repeated in the pre-randomization interval (within 6 weeks prior to randomization). If not possible (e.g. denied by insurance), other tests can be substituted that will evaluate the breast and will address any new signs/symptoms. Mammogram and ultrasound may be unilateral (affected side) or bilateral, at physician discretion. Breast imaging is not required if the breast is replaced by tumor or ulcerated in a way that makes breast imaging not feasible. If so, physical exam documentation must reflect this. A physical exam can only be used for pre-randomization evaluation of the breast if imaging is not feasible and tumor is palpable: in this case, physical exam findings describing the tumor must be documented. During follow-up breast imaging studies with mammogram OR ultrasound OR MRI need to be performed.

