Rev. 4/14 10. If the patient is being registered >4 weeks after initiation of systemic therapy, and the test was not performed within the baseline window (8 weeks before to 4 weeks after start of systemic therapy), physician may declare (if appropriate) that test was not indicated, and the patient may still be registered.

Rev. 4/14 11. Window is +/- 14 days for each QOL administration time point (**except step 2 randomization**).

Rev. 4/14 12. Window is \pm 14 days.

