Secondary objectives include comparison of proportions of patients with uncontrolled chest wall, time to uncontrolled chest wall disease and HRQL between arms. The proportion of patients with uncontrolled chest wall at 18 and 30 months post randomization will also be compared using the two-point procedure described in Freidlin, Korn, and et. al. (51). The fraction of uncontrolled chestwall at 6 months post randomization will also be compared using Fisher's exact test. HRQL scores will be compared using the methods described below.

Rev. 4/14

Rev. 4/14

Rev. 4/14	8.6	HRQL Power Estimate and Analysis Plan
Rev. 4/14		Health Related Quality of Life (HRQL) will be assessed using the FACT-B TOI, FACT-G, FACT Breast cancer subscale score and the additional items added to the Breast Cancer Subscale. The average total score for each scale will be recorded for both arms at baseline, randomization, six months post-randomization, 18 months post-randomization, and 30 months post-randomization and their change over time will be compared using mixed effects models. More specifically, we will fit a model with treatment assignment, assessment time, treatment assignment by assessment time interaction and other possible predictors. If the interaction of treatment assignment and assessment time is significant, then the change of HRQL over time would be different for the two arms. This model also accommodates inter-patient variability by modeling patient-specific regression lines. If there is high proportion of informative missingness in the HRQL data, we will analyze the data using the joint modeling of longitudinal data (here, HRQL) and survival time as described in Schluchter, 1992 and Schluchter, Greene and Beck, (55, 56). We will also test whether the HRQL increase or decrease from randomization to the time of decision for local therapy for the palliative local therapy arm, using a paired t test.
Rev. 7/13		
Rev. 4/14		The primary endpoint for HRQL is FACT-B TOI. Looking at FACT-B TOI data, using a 2-sided t test at level 0.20, there is 79% power to detect a difference of 4.5 points between the two arms with SD 14 (from E2100), assuming 69% of responders who received assigned treatment (89 per arm) have HRQL data at 18 months post-randomization. The Wilcoxon Rank Sum test will be used to compare the two arms if the scores are not normally distributed.
Rev. 4/14	8.7	Correlative Science (CTC) Power estimate

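### The Arm A decision-point HRQL form need only precede surgery, so a patient palliated with radiotherapy can complete it after treatment has begun

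*Combined protocol and SAP*

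**What the plan says.** Section 5.2 schedules an extra FACT-B + LS-9 form for Arm A patients at the point of decision for local therapy. It plans no formal comparative analysis of these data and gives their purpose: "it will serve to document the degree of symptoms that trigger the decision for palliative therapy in the control arm". The timing table in 5.2 labels the column "At decision for early local therapy (prior to surgery – Arm A patients only) (+/- 14 days".

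Section 7.1 places a QOL assessment in the calendar column for the Arm A decision. Footnote 11 states "Window is +/- 14 days for each QOL administration time point" and exempts only Step 2 randomization.

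Section 5.1.2.1 describes Arm A palliative local therapy: "It may consist of radiotherapy alone, surgery alone, or the combination".

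Section 5.2.1.3 covers how forms are given. For clinic forms it says "Whenever possible, the HRQL assessment should be administered at the clinic visit before the patient is seen by the physician". If the form is not given in clinic, "the HRQL data can be collected by telephone or mail as backup methods provided that HRQL data is captured prior to initiation of treatment".

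Section 8.2.2 lists the change in QOL from randomization to this decision as a measure for the palliative arm. Section 8.6 adds the analysis, a paired t test within that arm: "We will also test whether the HRQL increase or decrease from randomization to the time of decision for local therapy".

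**The concern.** A form meant to capture the symptoms that lead to palliative treatment has to be completed before that treatment starts. The only limit in the table is surgery, but the plan allows palliation without surgery, or with radiotherapy before it. For those patients the limit gives no protection against a form completed during or after radiation.

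Such a score is no longer a record of the trigger. Symptom relief from radiation would understate the symptoms that led to the decision, and acute radiation effects would overstate them. This is the plan's only patient-reported measure tied to the palliation decision. Section 8.6 does not exclude forms completed after treatment starts, and a late form cannot be collected again.

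**Working it through.** The plan gives no figure for this time point, so the check sets the timing rules side by side.

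**1. Which treatment sequences does the table's limit cover?** Section 5.1.2.1 does not fix the order of combined treatment, so there are four cases.

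| Arm A palliative treatment | Must the form precede all local treatment under the 5.2 table? |
|---|---|
| Surgery alone | Yes |
| Surgery, then radiotherapy | Yes |
| Radiotherapy, then surgery | No: it may follow the start of radiotherapy |
| Radiotherapy alone | No: there is no surgery for it to precede |

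**2. Does another rule close the two open cases?**

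- Section 5.2.1.3, telephone or mail: yes. Capture before treatment starts is a condition of using these methods.
- Section 5.2.1.3, clinic: no. The form should come before the physician is seen at that visit, whenever possible. The visit may itself fall during a radiotherapy course.
- Section 5.2.1.8: no. A form missed on a treatment date is completed at the rescheduled treatment, with no requirement that this be before the first fraction.
- Section 7.1, footnote 11: no. The 14-day tolerance applies on both sides of the decision. By contrast, the Step 2 QOL cell is exempt from the tolerance and carries footnote 7, "Collect prior to randomization". The decision-point QOL cell carries no such footnote.

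What remains open is clinic-administered forms in patients given radiotherapy alone or first.

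**3. How much treatment could fall inside the window?** The documents give no schedule for Arm A palliative radiotherapy. Section 5.3.4.1 sets five fractions a week, but 5.1.2.1 does not refer to Section 5.3. If that frequency is assumed, 14 days / 7 × 5 = 10 fractions could precede a compliant form when radiation starts at once, and 0 if it starts after day 14. The range is therefore 0 to 10 fractions.

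**4. Which analyses use the score?** The descriptive aim in 5.2, and the change defined in 8.2.2 and tested in 8.6. The primary HRQL comparison is FACT-B TOI between arms at 18 months and does not use this form. Its power statement is unaffected: 258 × 0.69 / 2 = 89 per arm, and 4.5 / (14 × √(2/89)) − 1.282 = 0.86, which gives about 80.6% power against the stated 79%.

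**The case against.** The strongest reply is that the time point is the decision itself, which comes before treatment, and that the 14 days is only a tolerance. Under 5.2.1.3 a form given at the decision visit is completed before the physician is seen, hence before the decision. Surgery-first patients and telephone or mail forms are already covered, and the sponsor states that no formal comparative analysis will use these data.

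Most of this stands, and it narrows the point. It does not close it, because the tolerance expressly allows a form up to 14 days after the decision and no text requires a clinic form to precede radiation. The stated limit on comparative analysis does not remove the paired test in 8.6.

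A reader might also infer that Arm A patients who cross over electively, without symptoms, complete this form and enter the paired test, because the 5.2 heading speaks of early local therapy, which the schema defines as Arm B. The documents do not support that. Footnote 3, attached to the 7.1 column, refers to a decision to deliver palliative local therapy and requires the reason to be documented. Section 6.3.2 ties the Arm A decision to the development of symptoms, and 5.1.2.1 limits Arm A local therapy to palliation. The heading is a labelling slip, and the words restricting it to Arm A patients show which event is meant.

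**Conclusion.** The point holds in a narrow form. For Arm A patients palliated with radiotherapy alone or before surgery, a clinic form completed after radiation has begun complies with the plan, and its score can enter the 8.6 paired test. This rests on reading the pre-treatment condition in 5.2.1.3 as its sentence is built, that is, as a condition on telephone and mail collection. If the sponsor meant it for every form, the main gap closes once the text says so.

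The size cannot be derived. The documents do not give the share of Arm A patients expected to receive palliative local therapy, the share of those given radiotherapy first, the share of forms completed late, or the effect of radiation on the score. Relief and toxicity act in opposite directions, so the sign is unknown too. A reader might be tempted to use the 4.5-point difference in 8.6 as the shift. That is the between-arm difference used for power, not a radiotherapy effect.

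The consequence is limited to one within-arm test and one descriptive aim. The correction is still worth making, because it costs almost nothing.

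**What to change.** - In the 5.2 table, and by a footnote to the matching column in 7.1, relabel the time point: *At decision for palliative local therapy (Arm A only), before the start of any palliative local therapy (surgery or radiation)*.
- For this time point, replace the symmetric tolerance in the table and in footnote 11 with a window from 14 days before the decision to the start of that therapy. A form completed at the decision visit before the physician is seen then still counts.
- Bring 5.2.1.3 and 5.2.1.8 into line, so that the pre-treatment condition covers clinic forms and the missed-visit rule does not override it here.
- In 8.6, limit the paired test to forms completed before local therapy starts.

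The cost is a column heading, a footnote and a few sentences. A few late forms would be lost to the paired test. These changes concern only when the questionnaire is collected and which forms are analysed. They do not alter clinical management.
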